**1.1 Research questions**

The implementation research study addressed three research questions:

Research question 1 (RQ1)	What are the program impacts on diet of adolescent girls : (1) dietary diversity, (2) less consumption of unhealthy snacks, and (3) meal frequency? [impact of integrating interventions into school-based platforms]
Research question 2 (RQ2)	What is the coverage and utilization of key adolescent nutrition interventions (classroom nutrition education, flag events/assemblies on nutrition, peer group mentoring, and Parent-Teacher meetings)? [outcome of integrating interventions into school-based platforms]
Research question 3 (RQ3)	What factors influenced the integration of adolescent nutrition interventions into school-based platforms and their outcomes and impacts? [pathway from integration of interventions to impact]

## 1.2 Impact evaluation study design

The impact evaluation of A&T's interventions used a cluster-randomized design with repeated cross-sectional surveys at baseline and endline. We applied stratified random allocation to 54 primary schools within 7 districts (*woredas*) across two regions (SNNP and Somali), which were assigned to either the A&T intervention schools (27 schools) or control schools (27 schools). A small baseline survey was conducted in October-November 2019, and the endline survey was conducted in March-May 2021 in the same 54 schools, thereby creating panel data at the school level (not at individual level). Program implementation duration was approximately 4 months (1 school semester); implementation faced major disruptions due to the COVID-19 pandemic throughout most of 2020, with state lockdown/restrictions and school closures, until schools reopened in October 2020.

## 1.3 Study sample

The primary study sample is adolescent girls (AG) aged 10-14 years and enrolled in grades 4-8 in the current school year. We estimated a total sample size of 540 girls (270 per arm) to detect a difference of 0.5 food groups in the mean dietary diversity score. Along with each AG, we included her parent/primary caregiver (N=540), given that parents and caregivers are usually responsible for purchasing and preparing foods for young adolescent girls.

Additionally, we interviewed school principals (1 per school), main science teacher (1 per school), and HEWs (1 per health post nearest to school). School checklists (1 per school) were conducted to assess any changes in school infrastructure and facilities, materials and supplies, operations, and staffing.

Table 1. Sample sizes

Survey respondent type	Baseline 2019		Endline 2021	
	Intervention	Control	Intervention	Control
Household survey:				
1 Adolescent girl	81	81	270	270
2 Parent/caregiver of adolescent girl	81	81	270	270
School principal/teacher survey or checklist:				
3 Principal (1 per school)	27	27	27	27
4 Science teacher (1 per school)	27	27	27	27
5 School checklist	27	27	27	27
Health worker survey:				
6 HEW (1 per school)	27	27	27	27
Total:	270	270	648	648

## II. Outcome Measures and Indicators

Outcome measures corresponding to the three research questions are presented below. Outcome measures under RQ 1 includes the primary outcome of the evaluation (i.e., used to test study hypotheses and arrive at a decision on overall study impact and to serve as basis to calculate the sample size); RQs 2 and 3 focus on secondary outcomes.

### 2.1 Research question 1 (impact on diets of adolescent girls)

For impact estimates, outcome measures related to adolescent diet will be used from the AG dataset only.

Table 2. Outcome measures for RQ1

Outcome	Indicator	Data source
Dietary diversity, consumption of unhealthy foods, and meal frequency	
Primary outcome:
 
 
- Dietary diversity score (# of food groups, out of 10 groups)
 
 
Secondary outcomes:
 
 
- % AG consumed unhealthy foods in past 24h (i.e., sweet foods and sweets, fried and salty foods, and sugar-sweetened beverages)
 
- Mean meal frequency score (# meals or snacks, out of 6 times)
 
	AG survey

## 2.2 Research question 2 (coverage and utilization)

For results on coverage and utilization of interventions, outcome measures will be used from the AG and Parent survey data. In the context of the overall evaluation, outcomes under this research question are considered as secondary outcomes.

Table 3. Outcome measures for RQ2

Outcome	Indicator	Data source
CORE INTERVENTIONS:		
Classroom lessons	
 
- % AG heard about nutrition in classroom in past 3 months
 
- % messages heard
 
	AG survey
Flag events/assemblies	
 
- % AG heard nutrition message during flag ceremony/assembly in past 3 months
 
- % messages heard
 
	AG survey
Student peer mentoring	
 
- % AG attended girls' club meeting on nutrition
 
- % messages discussed
 
- % AG attended mentorship meetings on nutrition
 
- % messages discussed
 
	AG survey
Parent-Teacher meetings	
 
- % Parents attend parents' meeting on nutrition
 
- % messages discussed
 
	Parent survey
OTHER INTERVENTIONS:		
BMI measurement and counseling	
 
- % AG received BMI measurement in past 3 months
 
- % AG received BMI/nutrition counseling in past 3 months
 
	AG survey
HEW home visits and contacts	
 
- % AG talked about nutrition with HEW in past 3 months
 
- % messages heard
 
- % AG talked about nutrition with community worker/WDA in past 3 months
 
- % messages heard
 
	AG survey, Parent survey
Community gatherings	
 
- % AG heard about nutrition in the community
 
- % source, messages heard
 
- % Parents heard about nutrition in the community
 
- % source, messages heard
 
	AG survey, Parent survey

## 2.3 Research question 3 (factors related to school, health, and home environment)

For assessing factors related to delivery of interventions, measures will be used from the school checklist and Principal and Teacher survey datasets. For additional behavioral determinants related to adolescent girls' diets, measures will be used from the AG and Parent survey datasets. In the context of the overall evaluation, outcomes under this RQ3 also count as secondary outcomes.

Table 4. Outcome measures for RQ3

Outcome	Indicator	Data source
Service provider capacity-building and service provision:		
School supplies and materials and operations	
 
- % schools with drinking water
 
- % schools with nutrition education materials
 
- % schools with clubs/mentorship programs
 
- % schools provide meal/foods
 
- % schools with break time for snack/lunch
 
	School checklist
Training and supervision	
 
- % P/T received training on adolescent nutrition
 
- % P/T received supervision on adolescent nutrition
 
- % HEW received training on adolescent nutrition
 
- % HEW received supervision on adolescent nutrition
 
	Principle/teacher survey, HEW survey
Principal/teacher and HEW knowledge and attitudes	
 
- % P/T perceived adolescent nutrition as a problem
 
- P/T adolescent nutrition knowledge score
 
- % HEW perceived adolescent nutrition as a problem
 
- HEW adolescent nutrition knowledge score
 
	Principle/teacher survey, HEW survey
Delivery of interventions	
 
- % P/T conducted parents' meeting on nutrition
 
- % messages discussed
 
- % P/T provided nutrition message during flag ceremony/assembly
 
- % message provided
 
- % P/T discussed nutrition during classroom lesson
 
- % message provided
 
- % P/T participated in girls' club/mentoring on nutrition
 
- % message discussed
 
- % P/T measured AG's BMI
 
- % P/T provided BMI/nutrition counseling
 
- % HEW provided adolescent nutrition counseling at HP
 
- % HEW measured BMI of AG, provided counseling
 
- % HEW conducted home visit and provided adolescent nutrition message
 
- % HEW visited school to advise about adolescent nutrition
 
- % HEW discussed adolescent nutrition at community gathering
 
	Principle/teacher survey, HEW survey
Behavioral determinants of AG and parents:		
School attendance and participation	
 
- % AGs missed school in past week, this year
 
- # of days missed school in past week, this year (reason)
 
- % AGs arrived late/leave early in past week, this year
 
- # of days arrived late/leave early in past week, this year (reason)
 
- % AG perceived school performance - poor/average/good
 
- % AG intention for more schooling – up to grade 12 or higher
 
	AG survey

Outcome	Indicator	Data source
Food environment	
 
- % received any free food or drinks at school
 
- # of shops/stalls selling fruits or veg on way to/from school
 
- # of shops/stalls selling packaged snacks on way to/from school
 
- # of shops/stalls selling fried foods on way to/from school
 
- % food groups available at home in past 7 days
 
- % junk foods available at home in past 7 days
 
- % schools with canteen, types of foods
 
- % schools with food vendors within 1-minute distance
 
	AG survey, Parents survey, School checklist
Parent-AG interactions	
 
- % AG interaction with parents
 
- % AG reported parental food control
 
- % Parents interaction with AG
 
- % Parents reported control of AG's foods
 
	AG survey, Parents survey
Parents' knowledge and attitudes	
 
- Parents adolescent nutrition knowledge score
 
	Parents survey
Parents' dietary and feeding behaviors	
 
- Parents' dietary diversity score
 
- % Parents consumed unhealthy foods in past 24h (i.e., sweets, fried and salty foods, and sugar-sweetened beverages)
 
- % Parents prepared food in past week, # of days (out of 7)
 
	Parent survey
AG's knowledge and attitudes	
 
- AG nutrition knowledge score
 
	AG survey
AG's other eating and snacking behaviors	
 
- % currently fasting, # of continuous fasting days
 
- % ate junk foods in past week, # of days (out of 7)
 
	AG survey

### III. Statistical Analysis Plan

#### 3.1 General principles and methods

Data analyses will be performed using STATA version 17.0 (StataCorp LLC). All applicable statistical tests will be two-sided to allow potential findings of unexpected effects. Statistical significance will be presented at levels of  $p<0.05$ ,  $p<0.01$ , and  $p<0.001$ .

A diagram presenting the flow of clusters and individuals through the trial, based on the Consolidation Standard of Reporting Trials (CONSORT) statement: extension to cluster randomized trials (1,2), is shown as follows.

[figure not shown]

Figure 1. CONSORT flow diagram for repeated cross-sectional surveys

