## 2.6 Sample Size

The primary study sample is adolescent girls enrolled in primary school and aged 10-14 years (grades 4-8). The sample size was estimated based on current prevalence of the primary outcome, the expected change after intervention, power to detect those differences (80%), and level of significance ( $\alpha=0.05$ ). As the intervention was randomized at the cluster level (54 clusters) rather than the individual level, cluster effect was considered for sample size calculation.

We used the number of food groups from the A&T Phase 1 endline survey for SNNPR (mean: 3.26, SD: 1.40, categorized as 9 food groups; Arimond et al., 2010), assuming an intra-cluster correlation (ICC) of 0.18. We calculated that a minimum sample of 189 girls per group will be able to detect a minimum of 0.6 food group consumption increase. The sample size at endline will be rounded to 270 girls per group so that 10 girls per school (2 per grade) will be sampled. Based on baseline data, we observed a mean of 3.69, SD: 1.56, categorized as 10 food groups. Assuming an ICC of 0.015, we estimated that this sample size will detect a minimum difference of 0.5 food groups.

School principals, science teachers and HEWs responsible for providing nutrition education or facilitating other related activities/interventions will also be included in both baseline and endline surveys.

At baseline, a light data collection at schools and subsamples of adolescent girls and their parents will be conducted to assess comparability between study arms. At endline, the full samples of adolescent girls and their parents will be surveyed (including those who participated at baseline).

Thus, the overall study samples are presented in **Table 3**.

Table 3. Sample sizes

	Baseline 2019		Endline 2021	
	Intervention	Control	Intervention	Control
Adolescent girls	81	81	270	270
Parents of adolescents	81	81	270	270
Principals (1 per school)	27	27	27	27

Science teachers (1 per school)	27	27	27	27
HEWs (1 per school)	27	27	27	27
Total	243	243	621	621

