### 4.4 Statistical methods

Data analysis will use econometric analysis to control for (any) differences at baseline and between intervention and comparison groups for all relevant variables of interest. Statistical testing for differences between the two groups will be done using a random effects regression, accounting for the clustering of errors within and across schools.

The randomized study design allows for the identification of causal effects of the adolescent nutrition intervention through comparisons of mean outcomes between the treatment and control groups. Key indicators will include dietary diversity. Impact will be assessed using “difference-in-difference” (DID) estimation and/or analysis of covariance (ANCOVA) controlling for covariates. Data management, data cleaning and statistical analyses will be conducted using Stata version 16 (Statacorp, USA). The statistical significance for tests will be set at 5% for main effects or 10% in case of interactions. All statistical tests will be one-sided.

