### 3.3 Impact estimates

The main analysis of impacts will be performed using intent-to-treat (ITT) specifications, wherein all study participants in the originally assigned program group at baseline are included in the statistical analysis and analyzed according to their program group, regardless of whether they received interventions or not. Respondents who refused or withdrew consent or those who are ineligible according to study protocol are excluded from ITT analysis.

The main impacts of the interventions will be estimated for: (1) dietary diversity score, (2) consumption of unhealthy foods/junk foods, and (3) meal frequency. Secondarily, impact will be estimated for exposure to the core interventions: classroom lessons about adolescent nutrition and healthy diets, flag ceremonies/assemblies to remind about key healthy eating messages, adolescent girls club/student peer mentoring on adolescent nutrition, and parent-teacher meetings to educate parents about adolescent nutrition and healthy diets. All impact indicators will be assessed among adolescent girls, except for the exposure to parent-teacher meetings which will be assessed from parents.

Given that the main impact indicators with full sample sizes were collected at endline only, linear regression models will be used to test the means of the outcome for estimates of group differences (intervention vs. control) at endline, with standard errors clustered at the school level. In the adjusted models, we will control for covariates such as adolescent girl age and other variables that differed between study arms. Robustness tests will be conducted using difference-in-differences analysis where outcome variables exist at baseline.

Table 6. Dummy table for impact estimates

Indicator	Baseline		Endline		Unadjusted impact est. 	Adjusted impact est. 
	A&T (N=)	Control (N=)	A&T (N=)	Control (N=)		
	Percent/Mean (SD)	Percent/Mean (SD)	Percent/Mean (SD)	Percent/Mean (SD)		
Dietary diversity score						
Consumption of unhealthy foods						
Meal frequency						

Controlling for clusters by school only.

Adjusted for AG age, household food security and wealth tertile, and clustered by school.

\*\*\* p<0.01; \*\* p<0.05; \* p<0.1

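### The star legend of SAP Table 6 marks p<0.1, although SAP 3.1 sets two-sided p<0.05 as the loosest significance level; the protocol's one-sided rule must be reconciled at the same time.

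*SAP*

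**What the plan says.** **SAP 3.1** fixes the direction of testing: "All applicable statistical tests will be two-sided to allow potential findings of unexpected effects". It continues: "Statistical significance will be presented at levels of" p<0.05, p<0.01 and p<0.001. The loosest level is therefore 0.05, two-sided.

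**SAP 3.3, Table 6**, is the dummy table for impact estimates. It has rows for dietary diversity score, unhealthy foods and meal frequency, each with an unadjusted and an adjusted estimate. Its legend assigns three stars to p<0.01, two to p<0.05 and one to p<0.1. The text above it says: "The main impacts of the interventions will be estimated for: (1) dietary diversity score, (2) consumption of unhealthy foods/junk foods, and (3) meal frequency".

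**SAP section II and Table 2** make the primary outcome the basis for deciding overall impact. They name only the dietary diversity score as primary and list unhealthy foods and meal frequency as secondary.

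**Protocol 4.4** says: "The statistical significance for tests will be set at 5% for main effects or 10% in case of interactions". It then adds: "All statistical tests will be one-sided". Protocol 2.6 sizes the trial at alpha 0.05 and 80% power without stating sidedness.

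**The concern.** The same SAP gives two sets of significance levels for the same estimates. An analyst who fills in Table 6 as printed will star results that 3.1 does not count as significant. The table shell names no column for a confidence interval or p-value, so as printed a one-star result could have p=0.051 or p=0.099.

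The 10% level has no source for these tests. The protocol allows 10% only for interactions. SAP 3.3 defines the main estimate as the difference between arms at endline, which is a main effect. Difference-in-differences, where the treatment effect is an interaction term, is only a robustness check there.

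At stake is how the primary result is marked, and whether the threshold is fixed in advance or can be chosen between two printed versions once the p-value is known.

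**Working it through.** **1. The levels side by side**

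| Source | Levels | Sides | Loosest level |
|---|---|---|---|
| SAP 3.1 | 0.05, 0.01, 0.001 | two | 0.05 |
| SAP Table 6 legend | 0.1, 0.05, 0.01 | not stated; two by 3.1 | 0.10 |
| Protocol 4.4, main effects | 0.05 | one | 0.05 one-sided |

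The literal difference within the SAP is that 0.1 appears in Table 6 where 3.1 has 0.001.

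**2. Which rule was the trial sized on?**

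Inputs from Protocol 2.6: "mean: 3.26, SD: 1.40, categorized as 9 food groups"; "assuming an intra-cluster correlation (ICC) of 0.18"; difference 0.6; power 80%; alpha 0.05; 27 schools per arm; stated result 189 girls per group.

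Girls per arm without clustering: n0 = 2 × [SD × (z_alpha + z_power) / difference]². With a fixed number of schools k: n = n0 × (1 − ICC) / (1 − ICC × n0 / k), then rounded up to whole girls per school.

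- Two-sided 5%: n0 = 2 × [1.40 × (1.960 + 0.842) / 0.6]² = 85.5. Then n = 85.5 × 0.82 / (1 − 0.18 × 85.5 / 27) = 162.9, or 6.03 girls per school. Rounded up to 7, this gives 7 × 27 = **189**, the stated figure.
- One-sided 5%: n0 = 2 × [1.40 × (1.645 + 0.842) / 0.6]² = 67.3. Then n = 100.2, or 3.71 girls per school. Rounded up to 4, this gives 4 × 27 = **108**, which does not match.

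The protocol does not print its formula, so the match is strong support for a two-sided 5% design rather than proof of it.

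**3. Which differences would be starred against 3.1?**

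Inputs from Protocol 2.6, updated with baseline data: SD 1.56, ICC 0.015, 270 girls per arm, 10 per school.

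SE = 1.56 × √[2 × (1 + 9 × 0.015) / 270] = 0.143.

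With 54 schools and school-clustered errors I use t on 53 degrees of freedom (my assumption):

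- p<0.10 two-sided: 1.674 × 0.143 = 0.24 food groups
- p<0.05 two-sided: 2.006 × 0.143 = 0.29 food groups

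Normal cut-offs (1.645 and 1.960) give 0.235 and 0.280.

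As a sensitivity check, keep the protocol's other planning pair together (ICC 0.18 with SD 1.40, on 9 food groups). SE = 1.40 × √[2 × (1 + 9 × 0.18) / 270] = 0.195, and the zone is 0.33 to 0.39.

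**4. Error rate of a star**

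With no true effect, the chance that one test earns at least one star is 10% under the Table 6 legend and 5% under 3.1.

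**5. The same zone under the protocol**

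The upper 5% point of t(53) is 1.674, which is also the two-sided 10% cut-off. A favourable difference above 0.24 therefore meets Protocol 4.4's one-sided 5% level. An unfavourable difference of the same size would be starred in Table 6 but is not significant under SAP 3.1, nor under a one-sided test for benefit.

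**The case against.** The best defence is that this is one legend on a dummy table, that it states openly what each star means, and that it changes no estimate or test. All of that is true. No text says that a star is the decision rule, so a reader might infer that non-significant effects will be claimed as findings, but the documents do not support that. What can be said is that such results would be starred when 3.1 does not count them as significant.

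A reader might also infer that the p<0.1 star breaks the protocol. For a favourable effect it does not, because 5% one-sided and 10% two-sided share a cut-off. The protocol's 5% cannot be cited against Table 6 without its one-sided statement. This does not rescue the legend: SAP 3.1 chose two-sided tests, and a two-sided p<0.1 star also marks effects in the wrong direction.

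A third tempting reading is that a star on any of the three rows would count as programme impact, with a chance of at least one false star of 1 − 0.9³ = 27% against 1 − 0.95³ = 14%. That assumes independent outcomes, although all three are eating measures from the same girls. It also treats two secondary outcomes as decisive, which SAP section II and Table 2 rule out. The phrase main impacts in SAP 3.3 can fairly be read as separating diet outcomes from the exposure outcomes that follow. Labelling the rows in Table 6 is a tidy-up, not a missing decision rule.

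Finally, a table shell need not list every column, so the absence of a confidence interval or p-value there is not itself a contradiction.

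**Conclusion.** The contradiction within the SAP stands: 3.1 and the Table 6 legend give different loosest levels for the primary result, and both are current text. Its practical size is a band of about 0.24 to 0.29 food groups (SD 1.56, ICC 0.015, 270 per arm, 53 degrees of freedom), or 0.33 to 0.39 with SD 1.40 and ICC 0.18. The false-star rate on a single test is 10% rather than 5%. Alongside it is a conflict between the documents on sidedness, under which a favourable result in that band is significant by the protocol and not by the SAP. The reproduction of 189 favours two-sided 5% as the common rule. The primary outcome itself is already clearly designated. This is a cheap correction that should be made, not a flaw that threatens the trial's validity.

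**What to change.** 1. Replace the Table 6 legend with the three levels of SAP 3.1. Alternatively, drop the stars and show for each row the estimate, the school-clustered 95% confidence interval and the exact p-value.
2. State one rule for the dietary diversity score, two-sided 5%, in both SAP 3.3 and Protocol 4.4, and amend the protocol's one-sided statement accordingly.
3. Label unhealthy foods and meal frequency as secondary in Table 6, in line with SAP section II and Table 2.

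The cost is wording and one table footnote. No data, sample size or model changes. Results with two-sided p between 0.05 and 0.10 lose their star.

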### 3.2 Sample characteristics

Baseline and endline characteristics will be reported between randomized program groups (A&T and control). For household samples, indicators of the adolescent girl characteristics (age, grade), parent's characteristics (age, marital status, education, occupation, religion), and household characteristics (member composition, food security, livelihood, and socioeconomic status). Binary variables will be summarized as proportions, and continuous variables will be summarized as mean values with standard deviations (when normally distributed) or as median with interquartile range (for non-normal distribution variables). T-test will be used to compare and infer significant difference between the program groups by survey round.

Table 5. Dummy table for sample characteristics

Indicator	Baseline		Endline	
	A&T (N=)	Control (N=)	A&T (N=)	Control (N=)
	Percent/Mean (SD)	Percent/Mean (SD)	Percent/Mean (SD)	Percent/Mean (SD)
Age of respondent (years)				
Marital status				

Education level				
Occupation				
Religion				

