### 1.3 Trial design

The evaluation will use a two-arm cluster-randomized, non-masked trial design, consisting of two cross-sectional surveys at baseline and endline. The unit of randomization is the primary school which includes grades 1-8. The baseline survey will take place in October-November 2019 (when the school year begins), and the endline survey will place in March-April 2021 (following the end of first semester classes). Program implementation was halted from March to October 2020 due to the COVID-19 pandemic, thus the endline survey was postponed to the following school year after implementation was reinitiated. The study design will allow us to assess the impact of adolescent nutrition interventions delivered through school on adolescent girls aged 10-14 years enrolled in grades 4-8.

[figure not shown]

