## III. Methods: Assignment of Interventions

### 3.1 Allocation

A cluster is defined as the primary school that includes grades 1-8. Four woredas in SNNPR (with 31 schools) and three woredas in Somali region (with 23 schools), i.e., one school under each woreda school supervisor, were selected as potential intervention areas (see **Figure 3**). (Within woredas, there are designated supervisors at the education office who are responsible for supervising 1-7 schools. Supervisors are responsible for visiting schools one day per week (less frequently in the Somali region) and are provided with a checklist to ensure that schools are operating effectively. As feasible, we tried to select one school under the responsibility of a (unique) supervisor, to avoid study contamination and confusion among supervisors in conducting their duties.) The samples across the two regions will be pooled to estimate effects at program level. We will use stratified randomization within woreda to try to balance potential co-interventions and confounders. Then 27 schools will be allocated to the intervention arm and 27 schools will be allocated to the control arm by use of computer-generated pseudo-random numbers.

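### SAP 3.2 compares characteristics between arms with a plain t-test that ignores school clustering and woreda stratification, so its p-values can be wrong in either direction

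*SAP*

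**What the plan says.** Protocol 1.3: "The unit of randomization is the primary school which includes grades 1-8". Protocol 3.1 adds that "27 schools will be allocated to the intervention arm and 27 schools will be allocated to the control arm", and also "We will use stratified randomization within woreda to try to balance potential co-interventions and confounders". There are seven woredas.

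Girls are sampled within those schools. Protocol 2.6: "The sample size at endline will be rounded to 270 girls per group so that 10 girls per school (2 per grade) will be sampled". The sample-size row for girls in SAP 1.3 reads "1 Adolescent girl 81 81 270 270" (baseline intervention and control, then endline intervention and control), so baseline has 81/27 = 3 girls per school per arm. One parent is interviewed per girl.

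On comparing the arms' characteristics, SAP 3.2 says: "T-test will be used to compare and infer significant difference between the program groups by survey round". That is all it says about the test.

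Elsewhere the plan does allow for schools. SAP 3.3 fits the impact models "with standard errors clustered at the school level". SAP 3.3.1 accounts for school clustering in the pathway comparisons. Protocol 4.4 describes testing between the groups by random effects regression that allows for clustering. SAP 3.2 is the exception.

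**The concern.** A two-sample t-test treats the 162 baseline girls or 540 endline girls as independently allocated. Whole schools were allocated, and pupils of one school tend to share livelihood, wealth and religion. The test then usually understates the standard error of the difference between arms. Stratification by woreda works the other way: it removes most of the between-woreda variation from the difference, but the t-test leaves that variation in its standard error.

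Two uses of the result are at stake. First, protocol 2.6 gives assessment of comparability as the reason for the baseline survey, and SAP 3.2 intends to infer significance from this test. Second, the text of SAP 3.3 adjusts for variables found to differ between arms, without saying how that is decided. SAP 3.2 is the only comparison of characteristics that the SAP sets out, so an invalid test could influence which covariates enter the adjusted model.

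**Working it through.** **Inputs.** 27 schools per arm (protocol 3.1). m = 3 girls per school at baseline and 10 at endline (protocol 2.6, SAP 1.3). Protocol 2.6 gives two ICCs for dietary diversity: one for planning ("assuming an intra-cluster correlation (ICC) of 0.18") and one of 0.015, stated next to the baseline results. Tests are two-sided at 5% (SAP 3.1; protocol 4.4 says one-sided, a separate conflict).

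**The plan's own figure first.** The documents give no error rate for this test, but the sample size shows that the clustering inputs are read correctly. Individually randomised size per arm: 2 × (1.96 + 0.8416)² × 1.40² / 0.6² = 85.47. With 27 schools per arm, girls per school = 85.47 × (1 − 0.18) / (27 − 85.47 × 0.18) = 6.03. Rounded up to 7, this gives 7 × 27 = 189 per arm, the protocol's figure.

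**Error of the unadjusted t-test, variation between schools only.** Design effect DE = 1 + (m − 1) × ICC. True two-sided error at nominal 5% = 2 × [1 − Φ(1.96/√DE)].

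| Round | ICC | DE | √DE | True error |
|---|---|---|---|---|
| Baseline, m = 3 | 0.015 | 1.030 | 1.01 | 5.4% |
| Baseline, m = 3 | 0.18 | 1.360 | 1.17 | 9.3% |
| Endline, m = 10 | 0.015 | 1.135 | 1.07 | 6.6% |
| Endline, m = 10 | 0.18 | 2.620 | 1.62 | 22.6% |

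√DE is the factor by which the t-test's standard error is too small. For religion, livelihood or wealth the ICC could be higher; at an assumed 0.30 the rates would be 12.1% and 30.8%.

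**Effect of the woreda stratification.** Split the ICC into a school part ρs and a woreda part ρw. If the arms were exactly balanced within woredas, the woreda part would cancel from the difference, and the ratio of true to assumed variance would be 1 + (m − 1)ρs − ρw. For a total of 0.18:

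- Half between woredas (ρs = ρw = 0.09): baseline 1 + 0.18 − 0.09 = 1.09, error 6.1%; endline 1 + 0.81 − 0.09 = 1.72, error 13.5%.
- All between woredas (ρs = 0, ρw = 0.18): 1 − 0.18 = 0.82 in both rounds, error 3.0%.

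**Simulation check.** 54 schools were allocated within seven woredas, with 8,000 runs per setting; the number of study schools in each woreda was assumed. At ICC 0.18:

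| Share of ICC between woredas | t-test, baseline | t-test, endline | School means, baseline | School means, endline |
|---|---|---|---|---|
| None | 9.1% | 22.8% | 5.2% | 4.9% |
| Half | 6.4% | 13.4% | 3.3% | 1.9% |
| All | 3.9% | 3.7% | 1.9% | 0.2% |

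At ICC 0.015 with no woreda share, the t-test gave 5.1% and 5.9%. The all-woreda rates lie a little above 3.0% because balance cannot be exact everywhere: with 31 and 23 schools in the two regions, at least one woreda in each has an odd number. The last two columns show that a t-test on school means restores about 5% only when there is no woreda component. The replacement therefore needs woreda terms as well as clustering.

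**The case against.** The strongest reply is that the problem may be small. At the ICC of 0.015 the error is 5.4% and 6.6%, close to nominal. At baseline, the round intended to show comparability, it stays below 10% even at 0.18. Some traits plainly differ by region: protocol 2.1 reports 38% pastoral in Somali against less than one percent in SNNPR. For such traits stratification may make the t-test conservative. All of this stands, and it limits the size of the point. It does not make the test valid: the direction and size of the error vary by characteristic, and a reader of the p-values cannot tell which case applies. The 0.015 is also uncertain support. With SD 1.56 and 270 per arm it gives a two-sided detectable difference of about 0.40 food groups, not the stated 0.5.

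A reader might infer that many chance differences will be declared significant. Applying 0.18 to all 11 characteristics named in SAP 3.2 gives 11 × 0.226 = 2.5 false findings at endline, against 11 × 0.05 = 0.55. The documents do not support that count. It uses one dietary ICC for every item, takes the larger of two values and ignores stratification. It also includes grade, which is balanced by design if two girls per grade are sampled. At 0.015 the same sum is 11 × 0.066 = 0.7.

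A reader might also infer that the t-test determines the adjusted impact model. SAP 3.3 does not say so, and footnote 2 of its Table 6 gives a fixed set: age of the girl, food security of the household, and wealth in tertiles. Text and footnote disagree, so the risk is real but limited.

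Using a t-test for multi-category or skewed variables is a lesser matter; no distortion from that has been shown.

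**Conclusion.** The concern holds as a defect of method and of consistency. SAP 3.2 disregards the randomised unit and the stratification, contrary to SAP 3.3, SAP 3.3.1 and protocol 4.4. Over the protocol's two ICCs, the true error of a nominal 5% comparison is about 5% to 9% at baseline and 7% to 23% at endline if the clustering is all between schools. It is lower, and can fall below 5%, if the variation is mainly between woredas.

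These ranges assume equal numbers per school, two-sided tests, and ICCs for dietary diversity carried over to other characteristics; the true values for those are not in the documents.

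The unadjusted impact estimate is not affected, because it uses school-clustered standard errors. Comparisons of principals, science teachers and health extension workers have one respondent per school, so there is no within-school clustering to ignore.

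**What to change.** In SAP 3.2, replace the t-test with a regression of each girl, parent and household characteristic on arm, with woreda indicators and school-clustered standard errors. Use a joint Wald test for variables with several categories. With 54 schools, state the small-sample correction. Alternatively, delete the sentence on testing and report balance descriptively; Table 5 already has no p-value column, so its layout need not change.

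In SAP 3.3, do not let unclustered p-values decide which variables count as different between arms. Make the text agree with footnote 2 of Table 6 by naming its three covariates as the adjustment set.

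The cost is SAP wording and a few lines of code. Usually fewer characteristics will be called different; for those that vary mainly by woreda, the corrected test may be more sensitive.
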